5.3 Treatment assignment

Treatment numbers will be assigned in ascending, sequential order to eligible patients (see Section 5.5.1 for details). The investigator will enter the Treatment number on the CRF.

5.4 Treatment blinding

This is an open label trial.

5.5 Treating the patient

5.5.1 Treatment / Patient numbering

Screening number

Each patient screened is assigned a unique screening number. The screening number is a combination of the center number, that is provided by Novartis, and a three digit number starting with 001 for each patient which is assigned by the Investigator. Therefore, if the center number is 1 (any leading 0's in the center number are dropped) the screening numbers will be assigned such as 1001001, 1001002, 1001003 in ascending order. If the center number is 2 (or 0002), the screening numbers will be 1002001, 1002002, 1002003 in an ascending order.

Treatment number

If the patient is deemed eligible for the study and will commence dosing, a treatment number will be assigned. Once assigned to a patient, a treatment number will not be reused.

The treatment number becomes the definitive patient number as soon as a patient receives the first dose of the respective study treatment.

There should be a source document maintained at the site which links the screening number to the treatment assignment number (once assigned). This source document should be provided to all appropriate parties (i.e., Central Laboratory, ECG Laboratory) as soon as this is available.

Commercially Confidential Information

5.5.2 Dispensing the study treatment

The investigational drug, CGF166 will be prepared by Novartis and supplied to the Investigator site as open labeled bulk medication in single dose septum vials.

For preparation of the study medication, please refer to the separate Pharmacy/Drug Delivery manual.

Appropriate documentation of the patient specific dispensing process must be maintained.

The medication labels will be in the local language, will comply with the legal requirements of each country, and will include storage conditions for the drug but no information about the patient.

5.5.3 Handling of study treatment

5.5.3.1 Handling of investigational treatment

Investigational treatment must be received at the study site by a designated person, handled and stored safely and properly, and kept in a secured location to which only the Investigator and designated staff have access. Upon receipt, the study drugs should be stored according to the instructions specified on the labels and in the Pharmacy/Drug Delivery Manual provided separately. Storage conditions must be adequately monitored and appropriate temperature/humidity logs maintained as Source data.

The Investigator must maintain an accurate record of the shipment and dispensing of study drug in a drug accountability ledger. Drug accountability will be noted by the Monitor during site visits and/or at the completion of the trial.

All drug supplies are to be used only for this protocol and not for any other purpose. Unless specifically instructed by Novartis, the Investigator must not destroy any drug labels, or any partly used or unused drug supply.

At the conclusion of the study, and, if allowed during the course of the study (e.g., an open label study), the Investigator will provide a copy of the drug accountability ledger to the Monitor.

Only after receiving a written authorization by Novartis, the Investigator/designee will send all the unused and partly used drug supplies as well as the empty containers to the address provided at the time of authorization for destruction or have the unused and partly used drug supplies as well as the empty containers destroyed by the site's pharmacist, providing a drug destruction certificate.

5.5.3.2 Handling of other study treatment

Not applicable.

5.5.4 Instructions for prescribing and taking study treatment

The dose prescribed and dispensed to the patient must be recorded on the Dosage Administration Record CRF including any observed leaking from the ear canal during dosing.

5.5.5 Permitted dose adjustments and interruptions of study treatment

Study drug dose adjustments and/or interruptions are not permitted, unless during surgical procedure the surgeon deems the patient ineligible or is unable to dose the patient.

In case of notable adverse events and safety concerns during dose escalation of the study, the following changes to the next planned dose level may be considered:

- Administration of a dose below the starting dose
- Administration of an intermediate dose between the current and preceding dose
- Administration of an intermediate dose between the current and next planned dose
- Repeated administration of the current dose
- Termination of any further dose escalation

These changes must be recorded on the Dosage Administration Record CRF.

5.5.6 Recommended treatment of adverse events

Medication used to treat AEs must be recorded on the Concomitant medications/Significant non-drug therapies CRF.

5.5.7 Rescue medication

Not applicable.

5.5.8 Concomitant treatment

All prescription medications, over-the-counter drugs and significant non-drug therapies (including physical therapy and blood transfusions) administered or taken within the timeframe defined in the entry criteria prior to the start of the study and during the study, must be recorded on the Concomitant medications/ Significant non-drug therapies section of the CRF.

Confidential

Medication entries should be specific to trade name, the single dose and unit, the frequency and route of administration, the start and discontinuation date and the reason for therapy.

5.5.9 **Prohibited treatment**

Use of known ototoxins, for example systemic aminoglycoside antibiotics, should be avoided if possible following dose administration through study completions. If a known, potent ototoxin should be required, for example cisplatin, then the patient may remain in the study but should be excluded from the efficacy analysis.

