The highest safe and tolerable volume determined in Part B will be used for IL-infusion in Part C patients. A total of 10 patients will be required for Part C of the current study. A safety review analogous to that described for parts A and B will take place whenever a block of five patients completes the first 4 weeks of study assessments.

Part A-C

Patients will undergo the same protocol-required assessments and visit schedule in all Parts of the trial (A-C). Part C of the study will only commence once preliminary safety and tolerability has been established for CGF166 and the associated delivery methods in patients in Part A and B.

The trial duration will consist of 63 day screening period followed by a 1-3 day baseline assessment period and in house surgical dose/post operation assessment period (~6-14 days) followed by a 6 month post-dose assessment period. In addition, all dosed patients in all Parts A-C will be advised of the opportunity to enroll in a separate protocol Commercially Confidential Information

During the screening period, eligibility of potential patients will be verified at the study centers.

Potential patients will be evaluated for fitness to undergoing protocol-required surgery and for the planned therapy based on physical exam, MRI, past/current medical history, and laboratory testing. During the screening period, potential patients will also undergo pre-treatment^{Commercially}, auditory and vestibular function tests.

At least two outpatient visits during the screening period are anticipated in order to complete the required verification and assessments. If all screening assessments can be completed in one visit, that is allowed. Additional outpatient screening visits (i.e., more than 2 visits) are permitted pending patients' and clinic schedule and the need for re-verifications and potential re-testing.

Based on the screening assessments, one ear will be selected as the study ear and will undergo the study required surgery; criteria for the selection of the study ear are described as follow:

- The ear with more severe hearing loss as determined by pure tone audiometry and speech recognition score
- If both ears have equal severity in hearing loss, then the study ear will be selected by the investigator's preference

Upon completing the screening visits, eligible patients will be scheduled for a baseline visit and surgery.

Baseline (Day -3 to -1)

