Eligible patients will return to the study center at baseline (Day -3 to -1) and undergo pre-operative preparation as well as pre-treatment functional assessments.

Day 1 visit

On Day 1, study patients will undergo the required protocol assessments and the stapedotomy for delivery of the study drug to the scala vestibuli perilymphatic space of the inner ear. At the completion of the surgery and study drug infusion, study patients will recover in the surgical center's post-op facility and undergo post-surgery evaluations and assessments. Study patients may be transitioned to either the inpatient unit of the surgical center or pre-arranged temporary housing close to the surgical center.

Day 2 to Day 6 visits

Study patients will be followed up for the next 5 post surgery days (Day 2 to Day 6) and will undergo the protocol-required safety follow up evaluations. Study patients will be discharged home if there are no significant adverse events requiring prolonged monitoring. Patients will have the option to remain in the provided housing until the completion of the Day 14 visit.

Subsequent visits will be scheduled with the study patients prior to being discharged.

Day 15 visit

Study patients will return to the study center to have surgical packing removed from their ear and will also undergo study required assessments. Patients will be discharged home or to their local housing at the end of all study required evaluations. Patients will be reminded of their next scheduled visit.

Follow up and end of study visits

Total follow-up period in the trial will be 6 months after administration of CGF166. The follow-up visits will be at 2, 4, and 6 months/EOS.

Patient who have already completed Day 169 assessment ($\sim 6 \text{ month}$) will return to site to complete end of study visit (visit 777) as soon as practically possible. Patients who have not completed Day 169 will complete end of study visit (visit 777) on Day 169.

During each visit to the study center, post-operative recovery of the study ear will be monitored and evaluated. Study patients will also undergo the study-required safety, Confidential Information

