4.2 Exclusion criteria

Patients fulfilling **any** of the following criteria are not eligible for inclusion in this study:

- 1. Use of other investigational drugs at the time of enrollment, or within 5 half-lives of enrollment, or until the expected PD effect has returned to baseline, whichever is longer; or longer if required by local regulations.
- 2. History of hypersensitivity to any of the study drugs or to drugs of similar chemical classes.
- 3. Patients with hearing loss caused by genetic/developmental disorders, e.g., cochlea aplasia.
- 4. Patients with existing conductive hearing loss or mixed hearing loss as judged by the Principal Investigator following a thorough review of all of the trial hearing assessments, air-bone gap assessment based on air and bone pure tone audiometry and MRI scan.
- 5. Patients with a history of cochlear implant in the study ear.

- 6. Hearing loss due to any other cause that would not be expected to respond to hair cell regeneration, for example trauma or central auditory lesions or lack of an auditory nerve
- 7. Patients who will require ototoxic drugs as routine therapy over the course of the study, for example cystic fibrosis patients.
- 8. Any contraindication to the planned surgery or anesthesia as determined by the surgeon, anesthesiologist, or designee.
- 9. Women of child-bearing potential, defined as all women physiologically capable of becoming pregnant, unless they are using highly effective methods of contraception during dosing and for 6 months following treatment period of the investigational medication. *Highly effective contraception methods include:*
 - Total abstinence (when this is in line with the preferred and usual lifestyle of the subject. Periodic abstinence (e.g., calendar, ovulation, symptothermal, post-ovulation methods) and withdrawal are not acceptable methods of contraception.
 - Female sterilization (have had surgical bilateral oophorectomy with or without hysterectomy) or tubal ligation at least six weeks before taking study treatment. In case of oophorectomy alone, only when the reproductive status of the woman has been confirmed by follow up hormone level assessment.
 - Male sterilization (at least 6 months prior to screening). For female subjects on the study the vasectomized male partner should be the sole partner for that subject.
 - Combination of any two of the following (a+b or a+c, or b+c):

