9.1 Analysis sets

For all analysis sets, patients will be analyzed according to the study treatment(s) received.

The safety analysis set will include all patients that received any study drug.

The PD analysis set will include all patients with available PD data and no protocol deviations with relevant impact on PD data.

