9.4.2 Statistical model, hypothesis, and method of analysis

Tone thresholds will be analyzed for each frequency tested separately.

For pure tone audiometry, a measure that depends on a patient being able to hear a tone, the following imputation will be done: If a patient is unable to hear the tone at a specific frequency it can be inferred that the threshold value exceeds the upper limit of the machine. In this case the value will be imputed to 5dB above the upper limit of the machine.

All pure tone audiometry air conduction threshold data will be listed and graphically displayed by patient, infusion volume, frequency, and visit/time. Summary statistics will be provided by infusion volume, frequency, ear and visit/time. Change from baseline of the thresholds (mean of screening and baseline visit) will also be summarized by infusion volume, frequency, ear and visit/time.

In addition, safety and tolerability is a co-primary endpoint, and will be analyzed as in Section 9.5.2 (Safety).

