9.4.3 Handling of missing values/censoring/discontinuations

All missing data, which are missing due to an assessment not having been made, will be treated as "missing at random". Patients with partial data will be included in the primary analysis. Where a missing data value occurs, this will be set to missing in the analysis. For the combined baseline of screening and baseline data, where only screening or baseline data is available, this value will be taken as the baseline. If no pre-treatment data is available, the subject will be excluded from the analysis when comparing the change to pre-treatment values.

Pure tone audiometry values which are missing because the hearing threshold exceeded the upper limit of the machine will be imputed with the value of 5dB above the upper limit of the machine.

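### The potent-ototoxin exclusion in Protocol 5.5.9 has no cut-off at first exposure, so as written it takes valid earlier audiograms out of the by-visit summaries (low priority)

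*Protocol*

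**What the plan says.** **The rule.** Protocol 5.5.9 asks that known ototoxins be avoided where possible from dosing until study completion. If a known, potent one is required (cisplatin is the example), "then the patient may remain in the study but should be excluded from the efficacy analysis". No date, visit or first-exposure limit is attached.

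**The analysis set.** Protocol 9.1 names a safety set and a PD set. The latter is also defined by patient: "The PD analysis set will include all patients with available PD data and no protocol deviations with relevant impact on PD data". SAP section 5 shows only the safety set; the rest is redacted.

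**The summaries affected.** Protocol 9.4.2, for pure tone thresholds: "Summary statistics will be provided by infusion volume, frequency, ear and visit/time". Change from baseline is summarised in the same way. The same section, and SAP 7.1.2, have all air-conduction thresholds listed and graphed.

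**Missing data.** Protocol 9.4.3 and SAP 7.1.3 keep patients with partial data, but their rule opens with "All missing data, which are missing due to an assessment not having been made". Neither mentions ototoxins.

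**Dates.** For each medication, Protocol 5.5.8 requires "the start and discontinuation date and the reason for therapy".

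**Eligibility.** Exclusion criterion 7 in Protocol 4.2 bars "Patients who will require ototoxic drugs as routine therapy over the course of the study, for example cystic fibrosis patients".

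**The concern.** Leaving out audiograms taken after a potent ototoxin is easy to defend, because the drug may itself change the threshold. Leaving out those taken before it is not: a later drug cannot have altered them, and the documents give no reason to discard them. The rule nevertheless removes the whole patient, so a first exposure at, say, Day 120 also empties that patient's Day 29, 57 and 113 entries in the summaries.

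Pure tone audiometry carries the primary efficacy objective, there is no control arm, and the infusion-volume groups are small, so one patient is a visible share of each summary. The loss is also avoidable, because the start date that would define a cut-off is already collected. A lesser point is that 5.5.9 does not define potent beyond its example. In an open-label study, whether a given drug triggers the rule could then be decided with the audiograms in view.

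**Working it through.** **Inputs.** Post-dose audiometry on Days 29, 57, 113 and 169 (Protocol assessment schedule), so 4 audiograms per patient. Protocol 9.4 and SAP 7.1 instead speak of 4-week intervals; I use the schedule. There are 13 air-conduction frequencies per ear (9.4.1). Planned sizes are 3 in Part A, 3 cohorts of 3 in Part B, and for Part C "A total of 10 patients will be required for Part C of the current study" (Protocol 3.1). SAP 2.2 carries other sizes for Parts B and C; I use those of Protocol version 06.

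**Plan's own figure.** 3 + 3 × 3 + 10 = 22, which matches the stated maximum enrolment.

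**Step 1: loss per triggered patient.** Valid audiograms discarded are those dated before first exposure.

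| First exposure | Valid audiograms discarded (of 4) | Study-ear thresholds (× 13) |
|---|---|---|
| Before Day 29 | 0 | 0 |
| Day 29 to 57 | 1 | 13 |
| Day 57 to 113 | 2 | 26 |
| Day 113 to 169 | 3 | 39 |

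A cut-off at first exposure would recover exactly these. If exposure is equally likely on any day from 1 to 169 (my assumption), the mean is (28 × 0 + 28 × 1 + 56 × 2 + 56 × 3) / 168 = 308 / 168 = 1.83 of 4, or 46%.

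**Step 2: share of the group.** The summaries are by infusion volume, not by Part. Protocol 5.2 gives Cohort 2 as 40 or 30 µL, so 0 to 3 of its planned patients are pooled with Part C.
- 30 µL: 10 to 13 patients, so one exclusion removes 1/13 to 1/10, or 7.7% to 10%.
- 20 µL (Cohort 1) and 60 µL (Cohort 4): 1/3, or 33%.
- 40 µL (Cohort 3 plus any of Cohort 2): 3 to 6 patients, so 1/6 to 1/3, or 17% to 33%.

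To give a sense of precision (the plan does not call for intervals on these summaries), the 95% half-width in SD units is t(0.975, n−1)/√n. From 10 to 9 patients it goes from 0.72 to 0.77; from 3 to 2, from 2.48 to 8.98.

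**Step 3: likelihood.** The documents give no exposure rate. For an assumed per-patient probability p, independent between patients, P(at least one of 10 Part C patients) = 1 − (1 − p)^10. The expected number of valid audiograms lost is 10 × p × 1.83, out of 10 × 4 = 40.

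| Assumed p | P(at least one) | Expected loss of 40 |
|---|---|---|
| 1% | 9.6% | 0.18 (0.5%) |
| 2% | 18.3% | 0.37 (0.9%) |
| 5% | 40.1% | 0.92 (2.3%) |

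**The case against.** The strongest reply has four parts.

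- **Redaction.** An efficacy or PD set with an exposure cut-off could sit in the hidden part of SAP section 5. This stands as a limit on the claim. It does not change the visible protocol rule, which has no cut-off and would then need aligning with the SAP.
- **The chain is inferred.** The efficacy analysis is not a defined set, nothing written ties 5.5.9 to the PD set, and a drug use after which the patient may stay in the study is not clearly a protocol deviation. The by-visit statistics come from Protocol 9.4.2; the visible SAP 7.1.2 only lists and graphs. This too stands in part, but 5.5.9 excludes the patient by itself, and 9.4.2 is where the consequence falls.
- **Preference.** The study is non-confirmatory and its visible analysis descriptive, and dropping whole patients keeps the same patients at every visit. That is a real advantage, but a small one: n already varies by visit under 9.4.3, and it can be shown.
- **Proportion.** The event is rare, and dosing in the 3-patient cohorts is complete (Protocol 5.2). This stands, and it sets the priority.

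A reader might also infer that 5.5.9 contradicts 9.4.3 and SAP 7.1.3. It does not: those sections deal with assessments that were not made, not with patients excluded after being assessed. Nor are the data lost to the study. Listings and graphs retain them, and Protocol 6.5.6 makes audiometry a safety assessment too, although 9.5.2 names no audiometry summary.

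**Conclusion.** The point holds at low priority. As the visible text reads, a potent-ototoxin exposure removes up to 3 of 4 valid post-dose audiograms for that patient, and one patient from the infusion-volume group at every visit. The share is at most 10% at 30 µL and 33% at 20 or 60 µL, at planned sizes. It rests on reading 5.5.9 literally and on redacted SAP section 5 holding no cut-off.

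Four stronger readings are not supported.
- **That 10 to 9 is the 30 µL denominator.** It is the Part C count; any Cohort 2 patients dosed at 30 µL enlarge the group.
- **That a complete six-month record would be discarded.** That needs an exposure after Day 169. Only patients already past Day 169 have such a gap, since it is they who "will return to site to complete end of study visit (visit 777) as soon as practically possible"; the others complete that visit on Day 169. Their number is not stated. Protocol 3.1 also treats the 6-month visit as the end of study, so whether the ototoxin window covers the gap is unclear.
- **That there is a substantial chance of it happening.** The 40.1% follows only from an assumed 5% rate. Over the assumed range, the expected loss stays below one of 40 audiograms.
- **That the rule biases the result one way.** Nothing in the documents gives a direction.

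**What to change.** Analysis only, with no change to patient care.

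- State, in Protocol 5.5.9 and 9.1 or in the SAP analysis-set and missing-data text, that a potent-ototoxin exposure alone does not remove a dosed patient from the efficacy (PD) set.
- Include all audiograms up to the recorded start date of the drug. Set later values to missing in the main summaries, and list and graph them with a flag.
- Show n at each visit.
- Fix the list of coded medications that trigger the rule before database lock.
- Optionally, add one sensitivity summary that includes the later values.

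**Cost.** A few sentences, some programming and no new data. The mix of patients can differ between visits. A change to protocol text needs a written amendment with the approvals in Protocol 11.1. If only the SAP is changed, it should say explicitly how it reads 5.5.9, so that the two documents do not conflict. For cohorts whose audiometry has already been reviewed, report the change as made after data review.

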5.5.10 Discontinuation of study treatment and premature patient withdrawal

Study and cohort "Stopping rules"

The study will be put on hold and no new patients dosed pending a full safety review if any of the following criteria should be met:

- 3 or more patients with study drug-related or surgical procedure-related SAEs are reported
- At least 2 patients in the same cohort experience a similar AE which is assessed as severe in intensity, and is related to the study drug or surgical procedure
- Clinical evidence of post-operative vestibular dysfunction of moderate severity (impairs instrumental activities of daily living, such as preparing meals or housework) that persists longer than 4 weeks in 2 patients.
- •

- 1 patient develops a severe systemic immune response attributed to study drug
- 1 patient develops a severe infection consistent with those caused by adenovirus (if confirmed to be related to study drug).

Individual patient withdrawal

Patients may voluntarily withdraw from the study for any reason at any time. They may be considered withdrawn if they state an intention to withdraw, fail to return for visits, or become lost to follow-up for any other reason.

Confidential

If a patient withdrawal occurs for any reason, the investigator must make every effort to determine the primary reason for a patient's withdrawal from the study and record this information on the CRF.

The investigator should withdraw the patient from study if, on balance, he/she believes that continuation would be detrimental to the patient's well-being. A patient may withdraw consent from the study at any time.

A decision to not administer the single dose study treatment and patient withdrawal will be at the discretion of the Investigator, under the following circumstances:

- Complication during surgery or patient ear anatomy does not allow the surgeon to properly administer the dose infusion
- Use of prohibited treatment
- Any other protocol deviation that results in a significant risk to the patient's safety

Patients who discontinue study treatment should NOT automatically be considered withdrawn from the study. As single dose gene therapy, every effort will be to follow up with all treated patients whom have discontinued for whatever reason. See Section 6 for the required assessments of these patients after discontinuation of study treatment.

For patients who are lost to follow-up (i.e., those patients whose status is unclear because they fail to appear for study visits without stating an intention to withdraw), the investigator should show "due diligence" by documenting in the source documents steps taken to contact the patient, e.g., dates of telephone calls, registered letters, etc.

Patients who are withdrawn from the study for reasons other than safety or lack of efficacy will not be replaced by an equal number of newly enrolled patients.

